## Descriptive Evaluation Analysis Plan

### The Evaluation of the Family Champions Project in Dallas, TX

#### A. Description of the intended intervention(s)

Anthem Strong Families' Family Champions Project (FCP) offers skill-building primary curriculum and support services to program participants. The evidence-based TYRO Leadership and TYRO Core Communication curricula, totaling 18 hours, are offered as group classes by trained facilitators in which low-income adults learn skills related to healthy relationships and financial wellbeing. Support services, including case management and additional, optional classes through Anthem's Mini-Clinic series, are available to all FCP participants.

The main intervention being tested in this descriptive evaluation is the multistep continuous quality improvement (CQI) cycle created by Midwest Evaluation and Research (MER) that aims to improve FCP program implementation. The content and components of each step in the process are described below.

#### 1. **Step 1: Real-Time Performance Assessment Reports (prepared and presented bi-weekly by evaluation lead and/or data manager)**

- a. Report description - use key indicators to track overall performance trends.
- b. Purpose –
  - i. Provide real time monitoring of data entry and progress toward key metrics
  - ii. Familiarize CQI team staff with metrics that will be monitored and discussed throughout the lifetime of the project and in subsequent reports (Steps 2-5)
- c. Fidelity tracking – number of CQI team meetings scheduled and held where Step 1 CQI reports are presented to the CQI team
- d. Dosage tracking -
  - i. Intended vs. actual amount received – attendance of all CQI Team members at meetings for Step 1 Reports (i.e., number, names, roles) documented on CQI Team Tracking Sheet
- e. Performance Intervention Tracking – CQI Tracking Sheet for Performance Issues and Interventions (ongoing entry and revision as needed)
- f. Feasibility Assessment –
  - i. Focus on utility and user-friendliness of Step 1 report
  - ii. CQI Team Survey for Step 1: administered each program year to permanent staff on the CQI Team

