- a. Report description – examine performance trends before and after an intervention at each site, looking for improvements and comparing to the relevant standards
- b. Purpose – assess results of interventions on performance outputs to determine whether improvements were made for the relevant standard
- c. Fidelity tracking –
  - i. Intended amount to be offered based on intended report timeline
  - ii. Actual amount offered (# CQI Team meetings scheduled on Outlook, # CQI Team meetings where Step 4 CQI Report presented to CQI Team, # Step 4 reports created)
- d. Dosage tracking –
  - i. Intended amount received – attendance of all members at CQI Team meetings for Step 4 Reports (i.e., number, names, roles)

- ii. Actual amount received – CQI Tracking Sheet for Team Attendance for Step 4 Reports
- e. Feasibility assessment –
  - i. Focus on utility and user-friendliness of Step 4 report
  - ii. CQI Team Survey for Step 4: administered each program year to staff on the CQI Team
  - iii. FCP Staff Survey for Step 4: administered each program year to all frontline staff who develop performance interventions with the CQI team

**Table 1.** Description of intended intervention components, content, dosage and implementation schedule, delivery, and focal populations

Components	Content	Dosage and schedule	Delivery	Focal population
CQI Process Step 1	Monitoring overall and recent program performance using nFORM operational reports, local evaluation survey data, and the query tool	Reports are prepared bi-weekly and discussed at bi-weekly, hour-long CQI team meetings	Virtual CQI team meetings are held bi-weekly on Tuesday mornings; the evaluation lead facilitates meetings, and Step 1 reports are presented by the evaluation lead and/or data manager	CQI team members (program director, program manager, evaluation lead, data manager(s))

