### **3. Data sources and data collection**

The data source for the program implementation and performance outcome measures is nFORM administrative data. Program staff are responsible for entering and updating client and workshop information, including workshop attendance and current client status, on an ongoing basis. These data are summarized bi-weekly in Step 1 CQI reports with metrics at the program level and annually in Step 2-4 CQI reports with metrics at the site level to monitor trends in program enrollment, workshop dosage, program attrition rates, and survey response rates.

The data source for participant outcomes related to healthy partner relationship attitudes is the nFORM

Healthy Marriage Adult Program survey, administered at orientation before the first primary workshop (entrance survey) and at the final primary workshop session (exit survey).

**Table 3.** Sources of data to address the research questions

Data source	Timing of data collection	Mode of data collection	Start and end date of data collection
nFORM administrative data	Ongoing	Program staff enter and update data related to enrollment, attendance, and client status	Start: April 2021 End: April 2025
nFORM Healthy Marriage Adult Program Survey	At orientation before the first primary workshop (entrance survey) and at the end of the final primary workshop session (exit survey)	Online via tablet or on paper as necessary	Start: April 2021 End: April 2025

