#### 4. Outcome measures

The main outcomes of interest addressed by the multistep CQI process are primary workshop dosage, participant attrition rates, and nFORM survey response rates, as these are key program performance metrics with targets set by the federal funders. The first research question looks at changes in each of these metrics over time overall across all service sites (program level), and the second research question looks at changes in each of these metrics over time broken down by service site for sites that focused on the same metrics. This will involve an assessment of any changes in metrics after intervention strategies were implemented, including whether performance targets were reached and whether improvements were meaningfully large. Potential ceiling and floor effects are mitigated during the process of selecting which metrics to attempt to improve via intervention strategies (i.e., metrics that are already at or close to targets are not selected for intervention); however, potential ceiling and floor effects will also be addressed by providing baseline data for metrics targeted for interventions at each service site.

The secondary research questions about participant-level attitude changes after program participation are assessed by constructing a composite measure calculated as the average of five nFORM survey items related to partner trust and intimacy. If more than one survey item within the composite is missing for a respondent, the value of the outcome measure will be set to missing.

**Table 4.** Outcomes used to answer the research questions

Research question	Outcome name	Description of the outcome measure	Source of the measure	Timing of measure
RQ1	Dosage	The outcome measure is the percent of target primary workshop hours received by program participants	nFORM operational report: Primary Workshop Participation Detail	Attendance is recorded after each workshop session
RQ1	Attrition	The outcome measure is the percent of program participants who leave the program without completing at least 90% of primary workshop hours	nFORM operational report: Client Status Summary	Ongoing

Research question	Outcome name	Description of the outcome measure	Source of the measure	Timing of measure

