**Family Champions Project
Statistical Analysis Plan**

Clinicaltrials.gov ID: NCT05298345

September 4, 2024

Analysis approach

To assess the association between the multistep CQI process and the outcome measures, trends in dosage, retention, and survey response rates will be assessed over time since the start of the program. If the CQI process has been effective in identifying and addressing issues that require intervention, we would expect that program implementation would get stronger over time, as measured by progress toward meeting programmatic targets for these measures.

Analytic sample

The analytic sample for RQ1 and RQ2 is made up of the participants who received services at the facilities that received CQI intervention efforts as part of the multistep CQI process. The aggregated dosage, retention, and survey response rate data for these participants will make up the analytic sample.

The analytic sample for the secondary research questions (RQ3 and RQ4) about participant healthy partner relationship attitudes will be defined as participants who have complete baseline and outcome data for the constructed outcome measure (complete case). Because these relationship questions are only shown to participants who report currently being in a romantic relationship, participants can only have complete case survey data if they report being in a relationship at both waves of data collection. As mentioned above, participants will only be included in the analytic sample if they have one or no missing values for the five items used to construct this outcome measure (80% or 100% of non-missing items). Participants who do not meet this threshold will have their outcome value assigned to missing and will not be included in the analytic sample; no imputation is planned for the outcome data.

Data preparation

Program-level and participant-level data will be downloaded as an Excel file using nFORM's data export feature. The data sets will be cleaned and prepared for analysis using the R Studio statistical software package. All files will be exported into R and cleaned separately before data sets are merged into a final, wide format file for analyses using nFORM client ID as the unique identifier for matching programmatic (dosage, client status, survey response rates) and participant survey data.

Analytic approach

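### CQI Step 1 monitors data entry, and dosage and attrition come from the staff-entered records, so more complete recording could look like a program-level improvement under RQ1

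*Protocol*

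**What the plan says.** Section A of the protocol states: "The main intervention being tested in this descriptive evaluation is the multistep continuous quality improvement (CQI) cycle". Step 1 of that cycle has two listed purposes, and the first is to "Provide real time monitoring of data entry and progress toward key metrics". Table 1 sets its frequency: "Reports are prepared bi-weekly and discussed at bi-weekly, hour-long CQI team meetings".

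Section B.4 names the main outcomes as "primary workshop dosage, participant attrition rates, and nFORM survey response rates, as these are key program performance metrics". On their source, section B.3 says: "The data source for the program implementation and performance outcome measures is nFORM administrative data". On who creates the records, it says: "Program staff are responsible for entering and updating client and workshop information, including workshop attendance and current client status". The same records feed the intervention: "These data are summarized bi-weekly in Step 1 CQI reports with metrics at the program level", with site-level summaries in Steps 2 to 4.

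Table 4 takes dosage (hours received as a share of target hours) from the Primary Workshop Participation Detail report. It takes attrition (leaving before reaching 90% of workshop hours) from the Client Status Summary. It also says that attendance is recorded after each session.

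The SAP's Analysis approach says that if CQI has been effective, "we would expect that program implementation would get stronger over time, as measured by progress toward meeting programmatic targets for these measures". Its Analytic approach plots monthly averages by enrollment month and reads them descriptively. Data preparation mentions cleaning and merging of exported files. It describes no measure of record completeness and no check against another source of attendance.

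**The concern.** Part of the intervention acts on the instrument that measures its outcomes. If staff who are reminded every two weeks about data entry leave fewer sessions unlogged as the grant proceeds, recorded hours can climb while attendance stays flat. Client status is exposed in the same way where a status was never updated or was set wrongly.

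RQ1 asks whether CQI supported changes in dosage and attrition, not in logging. The planned graph shows recorded values only, and the analysis has no comparator outside CQI. A reader of a rising line could not tell more hours attended from more hours entered. This goes beyond the usual limits of a before-and-after description, because better recording is itself an intended effect of Step 1.

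**Working it through.** **Inputs from the documents.** Six two-hour sessions and two three-hour sessions (Table 1); the 90% line in the attrition definition (Table 4).

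**Inputs assumed, because the documents give none.** True dosage *a*, constant over time, 60% to 90%. Share *c* of attended hours that is entered, 85% to 95% early and 98% to 99% late. Share *f* of missed hours falsely entered as attended, falling from 10% to 2%. An attended session never entered contributes zero hours; how nFORM treats it is not stated.

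**Step 1. The plan's own figure.** 6 × 2 + 2 × 3 = 18 hours, which reproduces the stated total. 90% of 18 is 16.2 hours.

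**Step 2. Fewer missing entries.** Recorded dosage = *a* × *c*, so the change is *a* × (*c* late − *c* early).

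| True dosage | Completeness | Recorded dosage | Change (points) |
|---|---|---|---|
| 60% | 95% to 99% | 57.0% to 59.4% | +2.4 |
| 75% | 95% to 99% | 71.25% to 74.25% | +3.0 |
| 75% | 90% to 98% | 67.5% to 73.5% | +6.0 |
| 75% | 85% to 98% | 63.75% to 73.5% | +9.75 |
| 90% | 85% to 98% | 76.5% to 88.2% | +11.7 |

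**Step 3. Fewer false entries.** The change is (1 − *a*) × (*f* late − *f* early). At *a* = 60%: 0.40 × (0.02 − 0.10) = −3.2 points. At *a* = 90%: 0.10 × (−0.08) = −0.8 points. The sign depends on which kind of error is being corrected.

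**Step 4. The 90% line.** A participant who attends everything but has one two-hour session unlogged shows 16/18 = 88.9%; with one three-hour session unlogged, 15/18 = 83.3%. Both fall below 90%, so all eight sessions must be logged. If each is logged independently with probability *c*, the chance is *c*⁸: 0.95⁸ = 66.3% and 0.99⁸ = 92.3%, a difference of 26 points with identical attendance. This bears on attrition only if the client status follows recorded hours, which the documents do not say.

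**Step 5. Which errors count.** Graphs are by enrollment month. Enrollment is expected to end on February 15, 2025, and data collection ends in April 2025. If one export is taken after that, an entry that was late but filled in beforehand has the same value as a prompt one. Only entries or statuses never made, or made wrongly, by the time of export can shift the trend. The export date is not stated.

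**The case against.** The strongest reply is that nothing shows under-recording ever occurred. Table 4 says attendance is recorded after each session, the documents give no completeness figure, and every magnitude above follows from chosen inputs. That stands: the effect is possible, not demonstrated.

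A reader might infer that the distortion tracks exposure to CQI and so also undermines RQ2. The documents do not support this. Step 1 is a constant two-weekly activity, and no period without it is described. What changes by site and date is the targeted intervention arising from the later steps, and data-entry monitoring is a stated purpose of Step 1 only. What remains is mainly a slow drift in the program-level series. RQ2's reading immediately after a targeted intervention is less exposed.

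A reader might also infer that prompter closing of client records biases attrition. With a late export it would not, for the reason in step 5 of the working. Nor is the bias necessarily in the favorable direction, as step 3 shows.

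The point does not extend to all three main outcomes. Survey response depends on participants completing a survey online or on paper.

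Finally, the SAP is modest: it speaks of association and describes trends, and section B.4 of the protocol adds baseline values, targets and whether improvements are meaningfully large. None of these separates recording from attendance, so the core point survives.

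**Conclusion.** The point holds as a limitation of RQ1 for dosage, and for attrition where statuses were never updated or were wrong. Each link is in the text: the intervention monitors data entry, program staff enter the records behind these outcomes, and improving trends are the expected sign of success, with no completeness check.

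Presence, size and direction cannot be determined from the documents. If unlogged attendance counts as zero and true dosage is constant between 60% and 90%, the assumed completeness gains would raise recorded dosage by 2.4 to 11.7 points. If the early errors were false entries, better recording would lower it by 0.8 to 3.2 points. It would go too far to say that the main conclusion is biased; the plan simply cannot rule the bias out. This is a cheap improvement, not a flaw that invalidates the evaluation.

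**What to change.** In the SAP's Data preparation and Analytic approach:

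1. Where the nFORM export or the workshop schedule identifies sessions held, do not score a held session with no attendance entry as zero hours.
2. By enrollment month and site, report the percent of held sessions with attendance entered and the percent of enrollees with a final client status, shown with the outcome graphs.
3. Use one final export, taken after data collection closes, for all cohorts.
4. Where completeness rises alongside the outcome, describe the RQ1 change as a change in recorded metrics that may partly reflect recording.

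No fixed completeness threshold is needed before a trend may be reported; the series beside the graph lets the reader judge.

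The cost is SAP wording and two derived series. They depend on held sessions being identifiable, which the documents do not confirm. Some early months may become hard to interpret. The series will not detect false entries, or one participant omitted from a session that was otherwise logged.

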#### 2. **Step 2: Performance Intervention Priorities Report (prepared and presented annually in quarter 2 of each grant year by evaluation lead)**

- a. Report description – compare overall performance trends by service site
- b. Purpose – target improvement efforts by setting site-specific priorities for interventions
- c. Fidelity tracking -
  - i. Intended amount of CQI to be offered based on intended report timeline
  - ii. Actual amount offered (# CQI Team meetings scheduled for Step 2 Reports on Outlook, # CQI Team meetings where Step 2 CQI Report was presented to CQI Team, # Step 2 reports created)

---

- d. Dosage tracking –
  - i. Intended amount received – attendance of all members at CQI Team meetings for Step 2 Reports (i.e., number, names, roles)
  - ii. Actual amount received – CQI Tracking Sheet for Team Attendance (See Appendix B) for Step 2 Reports
- e. Feasibility Assessment –
  - i. Focus on utility and user-friendliness of Step 2 report
  - ii. CQI Team Survey for Step 2: administered each program year to staff on the CQI Team
  - iii. Family Champions Project staff survey for Step 2: administered each program year to all frontline staff who help to develop targeted, site-specific interventions during staff meetings with leadership and with the CQI team on a rotating basis

**3. Step 3: Performance Intervention Strategy Report (prepared for each service site in quarter 2 of each grant year by evaluation lead)**

- a. Report description – use key indicators to track performance trends for each site individually
- b. Purpose – establish a performance intervention agenda for each site
- c. Fidelity tracking –
  - i. Intended amount to be offered based on intended report timeline
  - ii. Actual amount offered (# CQI Team meetings scheduled on Outlook, # CQI Team meetings where Step 3 CQI Report presented to CQI Team, # Step 3 reports created)
- d. Dosage tracking –
  - i. Intended amount received – attendance of all members at CQI Team meetings for Step 3 Reports (i.e., number, names, roles)
  - ii. Actual amount received – CQI Tracking Sheet for Team Attendance for Step 3 Reports
- e. Feasibility assessment –
  - i. Focus on utility and user-friendliness of Step 3 report
  - ii. CQI Team Survey for Step 3: administered each program year to staff on the CQI Team

**4. Step 4: Performance Intervention Results Reports (prepared annually in quarter 4 of each grant year by evaluation lead)**

- a. Report description – examine performance trends before and after an intervention at each site, looking for improvements and comparing to the relevant standards
- b. Purpose – assess results of interventions on performance outputs to determine whether improvements were made for the relevant standard
- c. Fidelity tracking –
  - i. Intended amount to be offered based on intended report timeline
  - ii. Actual amount offered (# CQI Team meetings scheduled on Outlook, # CQI Team meetings where Step 4 CQI Report presented to CQI Team, # Step 4 reports created)
- d. Dosage tracking –
  - i. Intended amount received – attendance of all members at CQI Team meetings for Step 4 Reports (i.e., number, names, roles)

- ii. Actual amount received – CQI Tracking Sheet for Team Attendance for Step 4 Reports
- e. Feasibility assessment –
  - i. Focus on utility and user-friendliness of Step 4 report
  - ii. CQI Team Survey for Step 4: administered each program year to staff on the CQI Team
  - iii. FCP Staff Survey for Step 4: administered each program year to all frontline staff who develop performance interventions with the CQI team

**Table 1.** Description of intended intervention components, content, dosage and implementation schedule, delivery, and focal populations

Components	Content	Dosage and schedule	Delivery	Focal population
CQI Process Step 1	Monitoring overall and recent program performance using nFORM operational reports, local evaluation survey data, and the query tool	Reports are prepared bi-weekly and discussed at bi-weekly, hour-long CQI team meetings	Virtual CQI team meetings are held bi-weekly on Tuesday mornings; the evaluation lead facilitates meetings, and Step 1 reports are presented by the evaluation lead and/or data manager	CQI team members (program director, program manager, evaluation lead, data manager(s))
CQI Process Step 2	Monitoring the same performance metrics as presented in the Step 1 report, but broken down by service site using nFORM operational reports, local evaluation survey data, and the query tool	Reports are prepared annually in the second quarter of each grant year and discussed at standing CQI team meetings and program staff meetings	Existing CQI team meetings are used to present and discuss Step 2 report findings; the evaluation lead facilitates the meetings and presents the Step 2 reports to the CQI team. Following the CQI team discussion, program leadership shares the Step 2 report findings with front line staff during staff meetings to solicit ideas for interventions	CQI team members (program director, program manager, evaluation lead, data manager(s); rotating front line staff member); Anthem program staff (case managers, facilitators, recruitment and retention specialists) who work at the sites being discussed in the Step 2 reports
CQI Process Step 3	Offering the same conclusions as the Step 2 report but focusing on one service site per Step 3 report; uses nFORM operational reports, local evaluation survey data, and the query tool	Reports are prepared annually in the second quarter of each grant year and discussed at standing CQI team meetings	Step 3 reports are sent to the program director who distributes each site's Step 3 report to the relevant program staff who work at that site	CQI team members (program director, program manager, evaluation lead, data manager(s)); program staff for specific sites (case managers, facilitators)

Components	Content	Dosage and schedule	Delivery	Focal population
CQI Process Step 4	Assessing the results of targeted interventions that were put in place at specific sites based on the findings of the Step 2 and Step 3 reports	Reports are prepared annually in the fourth quarter of each grant year and discussed at standing CQI team meetings	Existing CQI team meetings are used to present and discuss Step 4 report findings (e.g., did the targeted metrics improve after implementing interventions? Does the metric now meet relevant standards? Were there any challenges with the implementation of interventions? How did frontline staff, leadership, and facility staff find the intervention? ); the evaluation lead facilitates the CQI team meetings and presents the Step 4 reports to the CQI team. Program leadership share Step 4 report findings with frontline staff in staff meetings.	CQI team members (program director, program manager, evaluation lead, data manager(s)); program staff (case managers, facilitators, recruitment and retention specialists) who are able to 1) provide feedback on challenges and successes with the implementation of the intended intervention, 2) see the results of the intervention
Relationship skills workshops	Healthy relationships curriculum (TYRO Core Communication; TYRO Leadership)	A total of 18 hours, with six two-hour sessions occurring weekly (TYRO Leadership) plus two three-hour sessions occurring weekly (TYRO Core Communication)	Group lessons provided online via Zoom or in-person at service sites; two trained facilitators lead every session	Individuals in the greater Dallas-Fort Worth area with low income

**Table 2.** Staff education and training (initial and ongoing)

Component	Education and initial training	Ongoing training
Relationship skills workshop	All facilitators, case managers, intake specialists, and other members of the staff must complete the workshop as a participant before entering the certified TYRO Facilitator training component. Once the training is complete, each facilitator observes an experienced staff	Facilitators complete an annual refresher process to ensure curriculum fidelity. That process includes observations by the Program Manager, Program Director, or another qualified designee. We attempt to provide opportunities to become re-certified every two to three years. Other

Component	Education and initial training	Ongoing training
	prior to undergoing observation of their group facilitation. Once completed, they are considered a certified TYRO curriculum facilitator.	facilitation or case management training is offered through targeted webinars or staff development sessions.
CQI process	At the beginning of the grant cycle, Anthem held a 3-day training to discuss the specifics of the grant and evaluation, and the purpose and process of CQI were discussed in detail at this initial training. As new staff are onboarded, they receive an explanation of the purpose and process of CQI, both from program leadership and from more experienced staff.	The purpose and process of CQI is reinforced on an ongoing basis. Starting with more experienced staff who fully understand their day-to-day roles, frontline staff are invited to sit in on CQI team meetings on a quarterly rotating basis to help them understand the value of the CQI process and how their role fits into the larger picture. CQI report findings are discussed with staff at weekly staff meetings.

